If neutrophil count falls below 500/mcL or if platelet count falls below 50,000/mcL during cohort C, mercaptopurine will be held until recovery of neutrophil count above 750/mcL and platelets > 75,000/mcL.

For the first drop in ANC or platelets, resume MP at the same dose the patient was taking prior to the episode of myelosuppression.

If neutrophil count falls below 500/mcL or if platelet count falls below 50,000/mcL for a second (or greater) time, discontinue doses of MP

In the setting of liver dysfunction, with 6MP and oral methotrexate:

For increase in hepatic transaminases (SGPT/ALT or SGOT/AST) to greater than 5x ULN (Grade 3 toxicity), obtain total and direct bilirubin. Monitor SGPT/ALT, SGOT/AST and total and direct bilirubin as long as transaminases remain over 5x ULN.

Continue full dose therapy unless either of the following occurs:

- Direct bilirubin > 2 mg/dL

- SGPT/ALT or SGOT/AST > 20x ULN (Grade 4 toxicity) ~~on 2 determinations at least 1 week apart.~~
- If either of these occurs, hold mercaptopurine and monitor labs as above, weekly. Restart at full dose therapy when the transaminase elevation is < Grade 3 (less than 5x ULN), as long as direct bilirubin is < 2 mg/dl.

Exclude infectious hepatitis for persistent (> 1 month) Grade 3 elevations in SGPT/ALT or SGOT/AST above 5x ULN.

Consider discontinuing trimethoprim/sulfamethoxazole (TMP/SMX) in favor of an alternative approach to Pneumocystis prophylaxis and holding/modifying all other potentially hepatotoxic medications.

Cycle 2:

Patients who tolerate cycle 1 without DLT may have the option to repeat this cycle once. Cycle 2 may start on Day 15 – 22 of cycle 1.

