4.2 Dose Limiting Toxicity

Toxicity will be graded using the CTCAE criteria, version 4.03. The CTCAE provides descriptive terminology and a grading scale for each adverse event listed. A copy of the CTCAE can be downloaded from the CTEP home page (<http://ctep.cancer.gov>). Any dose-limiting toxicity (DLT) should be reported immediately through the TACL Operations Center to the Study Chair or Vice Chair. In addition to CTCAE, grading of sensory and motor neuropathies will be augmented by definitions listed in Appendix 5.

4.2.1 Definition of DLT: Dose limiting toxicity (DLT) will be defined as the occurrence of non-hematologic DLT and/or hematologic DLT as defined below.

4.2.1.1 Non-hematological DLT:

(Cohorts A and B) Any Grade 3 or greater non-hematological toxicity that is possibly, probably or definitely attributable to the protocol regimen and prevents a patient from receiving the required number of doses of therapy (as specified in Section 9.0) or from proceeding with further therapy by day 49 of the treatment cycle.

(Cohort C) Any Grade 3 or greater non-hematological toxicity that is possibly, probably or definitely attributable to the protocol regimen and prevents a patient from receiving the required number of doses of therapy (as specified in Section 9.0) or from proceeding with further therapy by day 21 of the treatment cycle for Stratum C.

4.2.1.2 Hematological DLT:

(Cohorts A and B) The absence of peripheral blood count recovery (ANC >500/ μ L and platelet count > 20,000/ μ L) 7 weeks (49 days) after the start of chemotherapy in the absence of persistent leukemia or documented myelosuppressive infection. Subjects with abnormal blood counts (Grade 1 through 4) at baseline due to disease will not be evaluable for hematologic DLT and will be considered not having had hematologic DLT for the purposes of the definition in 4.2.1.

(Cohort C) The absence of peripheral blood count recovery (ANC > 500/ μ L and platelet count > 20,000/ μ L) 3 weeks (21 days) after the start of chemotherapy in the absence of persistent leukemia or documented myelosuppressive infection. Subjects with abnormal blood counts (Grade 1 through 4) at baseline due to disease will not be evaluable for hematologic DLT and will be considered not having had hematologic DLT for the purposes of the definition in 4.2.1.

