4.3.1 Marqibo®

4.3.1.1 Weekly assessment of neurologic function should be performed prior to administration of Marqibo®. (Appendix 4).

- Subjects who develop grade 3 or greater sensory or motor neuropathy will discontinue Marqibo® treatment.
- Subjects with < grade 3 neuropathy will be closely monitored without any adjustment to Marqibo® dose

4.3.1.2 Dosing will NOT be held for cytopenias.

4.3.1.3 Transaminase elevation: Marqibo® dosing will be delayed for grade 3 or higher AST (aspartate aminotransferase) or ALT (alanine aminotransferase) elevation

until resolution to grade 2 or baseline, then resume full dose. Maximum allowable delays are specified in section 4.3.

4.3.1.4 Hyperbilirubinemia:

Bilirubin Level	Dose Delay
Total bilirubin < 1.5 x upper limit of normal and direct bilirubin < 1.4 mg/dL	None, administer full dose
Total bilirubin > 1.5 x upper limit of normal, and/or direct bilirubin \geq 1.4 mg/dL	Withhold dose until resolution to grade 1 bilirubin or baseline and direct bilirubin < 1.4, then resume full dose. Maximum allowable delays are specified in section 4.3.

For subjects with documented Gilbert's disease, no modification is necessary unless the total bilirubin exceeds 5 x ULN or the direct bilirubin is \geq 1.4 mg/dL.

4.3.1.5 Jaw Pain: Treat with analgesics; do not modify Marqibo® dose.

4.3.1.6 Extravasation: In the event of an extravasation, discontinue the IV administration of the drug and institute appropriate measures according to institutional guidelines.

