9.1 Endpoints

9.1.1 Primary Endpoint

Cohort A

The primary endpoint in Cohort A is whether a patient is successfully treated with UK ALL R3/Marqibo® at nearly full dose without inordinate delays in the resolution of hematologic and non-hematologic toxicity that preclude timely continuation with subsequent treatment.

Specifically, a patient will be considered successfully treated if:

- a. The patient has received 16 of 20 prescribed doses of Dexamethasone, 2 of 2 prescribed doses of Mitoxantrone, 3 of 4 prescribed doses of Marqibo®, and 1 of 2 doses of pegaspargase.
- b. The patient has not experienced a dose limiting toxicity (DLT) as defined in section 4.2.

A patient will be considered NOT successfully treated if (s)he has experienced a dose limiting toxicity (DLT) as defined in section 4.2, or has received fewer than the minimum numbers of prescribed doses as described in (a) above for reasons not unequivocally unrelated to treatment toxicity (see section 9.3.1)

Cohort B

The primary endpoint in Cohort B is whether a patient is successfully treated with UK ALL R3/Marqibo® without mitoxantrone at nearly full dose without inordinate delays in the resolution of hematologic and non-hematologic toxicity that preclude timely continuation with subsequent treatment.

Specifically, a patient will be considered successfully treated if:

- a. The patient has received 16 of 20 prescribed doses of Dexamethasone, 3 of 4 prescribed doses of Marqibo® and 1 of 2 doses of pegaspargase.
- b. The patient has not experienced a dose limiting toxicity (DLT) as defined in section 4.2

A patient will be considered NOT successfully treated if (s)he has experienced a dose limiting toxicity (DLT) as defined in section 4.2, or has received fewer than the minimum numbers of prescribed doses as described in (a) above for reasons not unequivocally unrelated to treatment toxicity (see section 9.3.1)

Cohort C

The primary endpoint in Cohort C is whether a patient is successfully treated with one cycle (14 days) of the modified maintenance treatment at nearly full dose without inordinate delays in the resolution of non-hematologic toxicity that preclude timely continuation with subsequent treatment.

Specifically, a patient will be considered successfully treated if during the first course of modified maintenance treatment:

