- a. The patient has received 8 of 10 prescribed doses of dexamethasone, and 1 of 1 prescribed doses of Marqibo®, 1 or 2 prescribed doses of Methotrexate, and at least 50% of doses of mercaptopurine
- b. The patient has not experienced a dose limiting toxicity (DLT) as defined in section 4.2

A patient will be considered NOT successfully treated if (s)he has experienced a dose limiting toxicity (DLT) as defined in section 4.2, or has received fewer than the minimum numbers of prescribed doses as described in (a) above for reasons not unequivocally unrelated to treatment toxicity (see section 9.3.1)

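### Cohort C: cycle 2 may start from day 15, before hematologic DLT can be judged, so for patients with unrecovered counts the no-DLT condition cannot yet be applied

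*Combined protocol and SAP*

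**What the plan says.** Section 4.1 (Cohort C, Cycle 2): "Patients who tolerate cycle 1 without DLT may have the option to repeat this cycle once. Cycle 2 may start on Day 15"; the window closes on day 22. No count or toxicity threshold is given for starting.

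Section 4.2.1 sets the Cohort C DLT time points:
- Non-hematologic: a related grade 3 or higher toxicity that prevents the required doses, or that prevents the patient "from proceeding with further therapy by day 21 of the treatment cycle for Stratum C".
- Hematologic: no recovery to ANC above 500/µL and platelets above 20,000/µL "3 weeks (21 days) after the start of chemotherapy", unless leukemia persists or there is a documented myelosuppressive infection. Patients whose baseline counts were abnormal because of disease are treated as having no hematologic DLT.

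Section 9.1.1 ties this to the primary endpoint: "The primary endpoint in Cohort C is whether a patient is successfully treated with one cycle (14 days) of the modified maintenance treatment". The success criteria refer to the first course. The failure sentence does not repeat that limit: "A patient will be considered NOT successfully treated if (s)he has experienced a dose limiting toxicity (DLT) as defined in section 4.2".

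On dosing, section 4.3.1.2 says of Marqibo: "Dosing will NOT be held for cytopenias". Section 4.3 allows no delays of study drugs for hematologic toxicity. Section 7.1 asks for a CBC within 1 day before Marqibo doses 2 to 4 in Cohorts A and B, but only twice weekly in Cohort C. Under section 7.3, a patient who receives cycle 2 needs only one restaging, on day 14 of that cycle.

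**The concern.** Entry to cycle 2 depends on a result that may not exist when cycle 2 starts. Followed literally, the plan lets an evaluable patient with an ANC of 300/µL on day 15 receive a second uncapped Marqibo dose. The same patient could be declared a cycle 1 hematologic DLT a week later, which is the status that should have barred the second cycle. By then the count reflects both cycles. Marrow status, needed to judge whether leukemia persists, may not be known.

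The second matter is how long a patient is followed for a cycle 1 non-hematologic DLT. A patient who waits can have one up to day 21. A patient who starts cycle 2 on day 15 has already gone on to further therapy, so a new event on days 16 to 21 can no longer meet the definition. The elective start date therefore sets the follow-up.

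Both matters feed the Cohort C condition in section 9.2, under which the cohort stays at dose level 2 if at most 2 of the first 6 evaluable patients are not successfully treated.

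**Working it through.** The plan gives no figure of its own on this point, so the check is a comparison of days, followed by an illustration.

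**Start days against the hematologic time point.** Permitted starts are days 15 to 22, which is 22 − 15 + 1 = 8 days.
- If 21 days after day 1 means day 22, starts on days 15 to 21 come before it: 7 of 8.
- If it means day 21 of the cycle, starts on days 15 to 20 come before it: 6 of 8.

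These are counts of dates, not of patients.

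**Which patients are affected.**
1. Cycle 1 drugs end on day 13 (mercaptopurine, section 4.1), so the required-dose limb is settled before day 15.
2. A start on days 15 to 21 is itself further therapy by day 21, so the other non-hematologic limb is settled too.
3. If a CBC at the start shows ANC above 500/µL and platelets above 20,000/µL, recovery is documented and the hematologic limb can reasonably be read as met.
4. Disease-related abnormal baseline counts remove the patient from the hematologic limb.
5. What remains is evaluable patients with ANC at most 500/µL or platelets at most 20,000/µL at a start before day 21 or 22. Section 3.3.2 admits patients with disease at the minimal residual level, so patients without disease-related abnormal baseline counts can be expected.

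**Drug given before the day 22 count after a day 15 start** (day 22 is then cycle 2 day 8):
- Marqibo: 1 of 1, so 2 × 2.0 = 4.0 mg/m² in total at dose level 2.
- Dexamethasone: 5 days × 2 = 10 of 10.
- Oral methotrexate: 1 of 2.
- Mercaptopurine: 7 of 13 by schedule. Section 4.1 holds it below ANC 500/µL or platelets 50,000/µL, so a patient with ANC 300/µL would not receive it.

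**Non-hematologic follow-up.** It is about 14 days with a day 15 start, against 21 days for a patient who waits.

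**Illustration only.** Suppose six independent patients. Let a be the chance of failing by day 14, and b the chance that a toxicity starting on days 15 to 21 blocks further therapy. A patient who waits fails with probability f = a + (1 − a)b; a day 15 starter fails with probability a. For a = 0.10 and b = 0.10, f = 0.10 + 0.90 × 0.10 = 0.19. Then:
- All wait: P(3 or more of 6) = 1 − [0.81^6 + 6(0.19)(0.81^5) + 15(0.19^2)(0.81^4)] = 0.087.
- All start on day 15: 1 − [0.9^6 + 6(0.1)(0.9^5) + 15(0.1^2)(0.9^4)] = 0.016.

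| a | b | f | All wait | Three start on day 15 | All start on day 15 |
|---|---|---|---|---|---|
| 0.10 | 0.05 | 0.145 | 0.043 | 0.027 | 0.016 |
| 0.10 | 0.10 | 0.19 | 0.087 | 0.042 | 0.016 |
| 0.10 | 0.20 | 0.28 | 0.220 | 0.080 | 0.016 |
| 0.20 | 0.05 | 0.24 | 0.154 | 0.125 | 0.099 |
| 0.20 | 0.10 | 0.28 | 0.220 | 0.153 | 0.099 |
| 0.20 | 0.20 | 0.36 | 0.373 | 0.216 | 0.099 |

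The values of a and b and the number of early starters are all assumptions; the documents give none of them.

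**The case against.** The strongest reply is that little is left open. Starting cycle 2 settles the non-hematologic limbs, a recovered count settles the hematologic one, and disease-related abnormal baseline counts take a patient out of it. That stands, and it limits the point to a subset. It does not answer the case of a patient who starts early with unrecovered counts.

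Several stronger readings are tempting, and the documents do not support them.
- A reader might infer that the no-DLT condition cannot be checked for anyone on 7 of the 8 start days. Those are dates, 6 of 8 on the other day count, and most patients on them may have a settled status.
- A reader might infer that the hematologic limb turns cycle 2 myelosuppression into a cycle 1 failure. Section 9.1.1 places the success criteria within the first course, and section 9.2 uses similar wording for the expansion. The failure sentence would only benefit from repeating it.
- A reader might take a grade 3 ALT rise as certain to be a DLT in a patient who waits and not in one who started early. For Marqibo, section 4.3.1.3 says "Marqibo® dosing will be delayed for grade 3 or higher AST" or ALT elevation. But section 4.1 continues full-dose mercaptopurine and methotrexate unless direct bilirubin exceeds 2 mg/dL or "SGPT/ALT or SGOT/AST > 20x ULN (Grade 4 toxicity". Further therapy is not defined as cycle 2 Marqibo, and cycle 2 is optional, so the classification is open.
- A reader might treat the table as the size of a bias. Its inputs are assumed. Section 9.2 also describes the design as non-prescriptive, provides for committee review, and has de-escalation considered after more than 1 failure in six, so 2 of 6 is not the only line.

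**Conclusion.** The timing conflict holds, and it is minor. Cycle 2 is conditional on no cycle 1 DLT, yet it may begin before hematologic DLT is judged, with no count threshold, no hold for cytopenia and no CBC required just before the second Marqibo dose. For evaluable patients with unrecovered counts at an early start, the condition cannot be applied and the later count is confounded by cycle 2 drugs. How many patients this covers cannot be derived from the documents.

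The shorter non-hematologic follow-up of early starters follows from the literal wording. It suits an endpoint about feasibility, since a patient who goes on to cycle 2 has shown that further therapy was possible. The report should still show how often it occurred and whether it matters to the count of six.

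The conclusion assumes that a recovered count at the start settles the hematologic limb, which section 4.2.1.2 implies but does not state.

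**What to change.** Add to section 4.2.1 (Cohort C), cross-referenced as an exception to sections 4.3 and 4.3.1.2:

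> If cycle 2 starts before day 22, cycle 1 DLT status is fixed on cycle 2 day 1, before Marqibo, using a CBC drawn within 1 day. Patients evaluable for hematologic DLT may start before day 22 only if ANC is >500/µL and platelets are >20,000/µL; otherwise they wait for recovery or for the day 22 assessment. Later events are tabulated under cycle 2.

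In section 9.1.1, repeat in the Cohort C failure sentence that the DLT must occur during the first course.

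Report how many patients had DLT status fixed early. Show the 2-of-6 count once more, with related grade 3 or higher non-hematologic toxicities that start by day 21 in early starters counted as failures. This is an upper bound, because it drops the requirement that the toxicity prevent therapy.

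Do not add a bar on cycle 2 for unresolved grade 3 non-hematologic toxicity. It would conflict with the section 4.1 instruction to continue full-dose oral therapy at grade 3 transaminase elevation, and it could create new DLTs by itself blocking therapy by day 21.

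**Cost.** One paragraph, a few words in 9.1.1 and one extra count. CBCs are already drawn twice weekly, so one draw is tied to cycle 2 day 1. A few patients with low counts wait up to 22 − 15 = 7 days, inside the existing window. A patient who proves to have a hematologic DLT at day 22 is already barred from cycle 2 by the plan's own rule.

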4.2 Dose Limiting Toxicity

Toxicity will be graded using the CTCAE criteria, version 4.03. The CTCAE provides descriptive terminology and a grading scale for each adverse event listed. A copy of the CTCAE can be downloaded from the CTEP home page (<http://ctep.cancer.gov>). Any dose-limiting toxicity (DLT) should be reported immediately through the TACL Operations Center to the Study Chair or Vice Chair. In addition to CTCAE, grading of sensory and motor neuropathies will be augmented by definitions listed in Appendix 5.

4.2.1 Definition of DLT: Dose limiting toxicity (DLT) will be defined as the occurrence of non-hematologic DLT and/or hematologic DLT as defined below.

4.2.1.1 Non-hematological DLT:

(Cohorts A and B) Any Grade 3 or greater non-hematological toxicity that is possibly, probably or definitely attributable to the protocol regimen and prevents a patient from receiving the required number of doses of therapy (as specified in Section 9.0) or from proceeding with further therapy by day 49 of the treatment cycle.

(Cohort C) Any Grade 3 or greater non-hematological toxicity that is possibly, probably or definitely attributable to the protocol regimen and prevents a patient from receiving the required number of doses of therapy (as specified in Section 9.0) or from proceeding with further therapy by day 21 of the treatment cycle for Stratum C.

4.2.1.2 Hematological DLT:

(Cohorts A and B) The absence of peripheral blood count recovery (ANC >500/ μ L and platelet count > 20,000/ μ L) 7 weeks (49 days) after the start of chemotherapy in the absence of persistent leukemia or documented myelosuppressive infection. Subjects with abnormal blood counts (Grade 1 through 4) at baseline due to disease will not be evaluable for hematologic DLT and will be considered not having had hematologic DLT for the purposes of the definition in 4.2.1.

(Cohort C) The absence of peripheral blood count recovery (ANC > 500/ μ L and platelet count > 20,000/ μ L) 3 weeks (21 days) after the start of chemotherapy in the absence of persistent leukemia or documented myelosuppressive infection. Subjects with abnormal blood counts (Grade 1 through 4) at baseline due to disease will not be evaluable for hematologic DLT and will be considered not having had hematologic DLT for the purposes of the definition in 4.2.1.

Adverse events (AEs) that are considered disease-related (not suspected of relationship to protocol specified therapy) will not be considered dose-limiting toxicities.

4.3 Dose Delays and Modifications

The intent of this study design is for all patients to receive and complete one course of therapy. Patients who exhibit signs of disease progression or experience an unacceptable toxicity will be discontinued from treatment. For Marqibo® dosing delays due to hepatotoxicity (see sections 4.3.1.3 and 4.3.1.4), a maximum delay of 7 days is allowed per dose and no dosing is permitted beyond day 35. There will be no dose delays or dose reductions of study drugs for hematologic toxicity during therapy. At the time that interim analysis is performed to evaluate toxicity (see sections 9.2 - 9.5), if it is determined that the regimen has excessive toxicity, protocol amendment may be considered to modify the dose of Marqibo®.

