Asparaginase Erwinia chrysanthemi (Erwinaze®), crisantapase (Erwinase®) asparaginase Erwinia chrysanthemi (recombinant)-rywn (Rylaze®) may be substituted for allergy to Pegaspargase. See below.

Drug Administration Details:

As per Cohort A, without mitoxantrone

Marqibo®

- Dose Level 1: 1.5 mg/m²/dose (no dose cap) given IV over 60 minutes (±10 minutes) on days 1, 8, 15 and 22.
- Dose Level 2: 2 mg/m²/dose (no dose cap) given IV over 60 minutes (±10 minutes) on days 1, 8, 15 and 22.
- Review list of concomitant medications that are prohibited (CYP3A4 inhibitors) or to be used with caution (Appendix 3). See section 4.5 for drug interactions.
- Dose will be given over 60 minutes ± 10 minutes

Other agents and instructions as detailed above in Cohort A, without mitoxantrone.

Cohort C: Modified Maintenance with Marqibo®

	Day 1	Day 2	Day 3	Day 4	Day 5	Day 8	Daily through day 13	Day 14
Marqibo®	●							Response Evaluator
Dexamathasone	●	●	●	●	●			
Methotrexate (PO)	●					●		
Mercaptopurine (PO)	●	●	●	●	●	●	●	
IT Methotrexate as needed no more than once weekly								

Marqibo®

- Dose Level 1: 1.5 mg/m²/dose (no dose cap) given IV over 60 minutes (±10 minutes) on day 1.
- Dose Level 2: 2 mg/m²/dose (no dose cap) given IV over 60 minutes (±10 minutes) on day 1.
- Review list of concomitant medications that are prohibited (CYP3A4 inhibitors) or to be used with caution (Appendix 3). See section 4.5 for drug interactions.
- Dose will be given over 60 minutes ± 10 minutes

Dexamethasone

- 6 mg/m²/day divided BID given orally on days 1 through 5. The two doses should be separated by at least 8 hours

- Any formulation of dexamethasone is acceptable

Methotrexate

- 20 mg/m²/dose given orally on day 1 and day 8.

Mercaptopurine

- 75 mg/m²/dose/day given orally, daily from days 1-13.

Intrathecal methotrexate

- Given intrathecally as needed, but no more than once weekly. Age-based dosing as below. Alternatively, per standard of care, ARA-C and hydrocortisone may be substituted if methotrexate is contraindicated.
- Timing of IT methotrexate is flexible in regard to timing of Marqibo®. However, these agents should not be given simultaneously in order to reduce the risk of administration route error.

Age (years)	Methotrexate (mg)
1-1.99	8 mg
2-2.99	10 mg
3-8.99	12 mg
≥ 9	15 mg

See appendix 8 for starting dose guidelines.

Dose modifications: (for patients without pre-existing disease related cytopenia)

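### Section 4.3 bars every dose delay or reduction for hematologic toxicity, which contradicts the Cohort C mercaptopurine rules in sections 4.1 and 6.7.4

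*Combined protocol and SAP*

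**What the plan says.** **The general rule.** Section 4.3 opens by addressing all patients and then states: "There will be no dose delays or dose reductions of study drugs for hematologic toxicity during therapy". No cohort or drug is exempted. Under the Marqibo heading, 4.3.1.2 adds a separate rule for that drug: "Dosing will NOT be held for cytopenias".

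**The Cohort C rule.** In section 4.1, mercaptopurine is part of protocol therapy at 75 mg/m² per day, "given orally, daily from days 1-13". A dose-modification block follows. It is limited to patients without pre-existing cytopenia due to disease. If ANC falls below 500/mcL or platelets fall below 50,000/mcL, "mercaptopurine will be held until recovery of neutrophil count above 750/mcL and platelets > 75,000/mcL". The next steps are set out too: "For the first drop in ANC or platelets, resume MP at the same dose"; and if counts fall below the thresholds "for a second (or greater) time, discontinue doses of MP".

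**The drug-information section.** Section 6.7.4 asks for TPMT status or thiopurine metabolites to be checked in patients with severe myelosuppression, so that the dose can be lowered where there is a TPMT defect.

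**The endpoint.** For Cohort C, 9.1.1 requires at least half of the mercaptopurine doses in the first cycle. A shortfall counts as unsuccessful treatment unless its cause is unequivocally unrelated to toxicity.

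**The concern.** Holding a daily drug because counts are low is a dose delay for hematologic toxicity. A site that takes 4.3 at its word would keep giving mercaptopurine to a neutropenic or thrombocytopenic child. A site that takes 4.1 at its word would stop. Nothing in either section refers to the other or sets an order of precedence.

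The first thing at stake is the safety of the individual patient. The second is that all sites should treat the same blood count in the same way. A more distant third is the primary endpoint: which rule a site follows changes how many mercaptopurine doses a patient receives, and 9.1.1 counts those doses.

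**Working it through.** The plan states no figure to reproduce here. The check is a comparison of texts, followed by hand arithmetic on the endpoint.

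**1. The instructions side by side**

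| Situation in Cohort C | Section 4.3 | Specific text | Conflict? |
|---|---|---|---|
| First fall below threshold, no prior disease-related cytopenia | no delay | 4.1: hold, then resume at the same dose | Yes, direct |
| Second or later fall | no delay or reduction | 4.1: discontinue | With the intent only; 4.3 itself requires discontinuation for unacceptable toxicity |
| Severe myelosuppression with a TPMT defect | no reduction | 6.7.4: reduce the dose | Yes, since the myelosuppression prompts the reduction |
| Pre-existing disease-related cytopenia | no delay | the 4.1 hold does not apply | No |
| Oral methotrexate or dexamethasone, low counts | no delay | 4.1 has no count rule | No |

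The last two rows show that 4.3 still does work in Cohort C. It should be narrowed, not removed.

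**2. Is 4.3 only a Marqibo rule?** Its wording is plural and covers study drugs in general. Marqibo has its own cytopenia rule in 4.3.1.2, which would then be redundant. Section 4.3.3.1 likewise does not reduce intrathecal methotrexate for myelosuppression. The policy therefore reaches beyond Marqibo.

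**3. The endpoint minimum.** Planned doses are 13 (days 1 to 13, section 4.1). Half is 0.5 × 13 = 6.5, so at least 7 must be taken. At 6 or fewer, the minimum is missed.

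**4. One hold.** Let s be the first day without a dose and r the day dosing resumes (r = 14 if it never does). Doses taken = 13 − (r − s). The minimum is missed when r − s ≥ 7. The table in 7.1 asks for blood counts twice weekly in Cohort C without fixing the days, so s is an assumption and a range is shown.

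| s | Resume day r | Doses taken | Minimum met? |
|---|---|---|---|
| 4 | 10 | 13 − 6 = 7 | Yes |
| 4 | 11 | 13 − 7 = 6 | No |
| 7 | never (14) | 13 − 7 = 6 | No |
| 8 | never (14) | 13 − 6 = 7 | Yes |

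A single hold that starts on day 8 or later cannot miss the minimum.

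**5. Two falls.** With counts assumed on days 4, 8 and 11 (hold on day 4, resume on day 8, discontinue on day 11), doses taken = 3 + 3 = 6, and the minimum is missed. If the middle count is on day 7 instead, doses taken = 3 + 4 = 7, and it is met. The result turns on one assumed day.

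**6. If one patient changed class among the first six.** A move from 1/6 to 2/6 meets the 9.2 condition for considering de-escalation (more than 1), yet stays within the condition in the same section for remaining at dose level 2 (at most 2 of 6). A move from 2/6 (33.3%, not more than 1/3) to 3/6 (50%) fails that condition and exceeds the one-third trigger for suspension and review.

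**The case against.** The strongest reply is that no site would be in real doubt. Section 4.1 gives Cohort C its own block with mandatory wording, thresholds, restart criteria and a second-fall rule. Section 4.3 offers one general sentence among sentences about Marqibo. The day-35 limit in the same paragraph fits the 28-day regimens rather than a 14-day cycle, and the drug subsections that follow do not list mercaptopurine. Most of this stands: the specific order would very probably be followed. It does not remove the contradiction. Section 6.7.4 sends the reader to the treatment section and the dose-modification section alike, and the general sentence in the latter says the reverse of 4.1.

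Three stronger readings are tempting, and the documents do not support them.

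- *Cytopenic children will be dosed through.* A reader might infer this from 4.3 alone, but it requires ignoring an explicit hold order. Section 4.3 also takes patients with unacceptable toxicity off treatment.
- *The primary endpoint is compromised.* If 4.1 is followed, no patient is reclassified. Otherwise, the conflict changes a classification only with an early and long loss of doses, and only if dosing through would have led to success. That is not assured, since absent count recovery "3 weeks (21 days) after the start of chemotherapy in the absence of persistent leukemia" can itself be a hematologic DLT under 4.2.1.2. Section 6.7.2 lists a decreased neutrophil count in more than 20% of patients on mercaptopurine, but as a general drug effect without a grade, so it is not a hold rate.
- *One reclassified patient would settle the dose.* Section 9.2 says its design is not prescriptive, and its triggers lead to review. The two different six-patient conditions in 9.2 are a separate matter that this conflict does not cause.

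**Conclusion.** Section 4.3 is wrong as written, and the fault is minor. Its unqualified sentence directly contradicts the mercaptopurine hold in 4.1 and the TPMT-based reduction in 6.7.4. It conflicts only in intent with discontinuation at a second fall. Section 4.1 is the natural governing rule, so 4.3 should change.

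The case rests on patient safety and uniform dosing, and confidence in the textual conflict is high. The effect on the 9.1.1 endpoint is only a possibility, confined to patients who lose at least 7 of 13 doses. The day-by-day examples rest on assumed blood-count days. No statement is made about how often such losses would occur.

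**What to change.** Add to the end of the sentence in 4.3: *except mercaptopurine in Cohort C, which is held, discontinued or reduced for low counts as specified in sections 4.1 and 6.7.4*.

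Reduction and section 6.7.4 need to be named. An exception limited to holding and discontinuation under 4.1 would still, read literally, bar the reduction for a TPMT defect. The clause leaves the general rule in force for the other Cohort C drugs. It also leaves the 4.1 hold restricted to patients without pre-existing disease-related cytopenia.

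No change to 9.1.1 is needed, because it already treats a toxicity-related shortfall in doses as unsuccessful treatment. The cost is one clause in an amendment, with no effect on endpoints, sample size, visits or data collection.
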